### **6.2.10.3 Routine Laboratory Parameters**

As outlined in the Time of Events Schedule, laboratory parameters will include CD4+ T cell counts and HIV-1 VLs, hematology, clinical chemistry, and urinalysis. ANA will be performed at screening.

Prior to each 3BNC117 or romidepsin infusion, pre-menopausal female volunteers will have serum beta-HCG assessed and at follow up visits they will have urine beta-HCG checked. The laboratory samples for these tests will be collected at the time points indicated in the Time of Events Schedule (Appendix A). In the event of an abnormal laboratory value, volunteers may be asked to have an additional sample collected at the discretion of the principal investigator or designee.

Volunteers will be screened for syphilis and viral hepatitis (HBsAg and HCV-RNA) at the Screening Visit.

### **6.2.11 Diagnostic work up in the event of graded elevations in total bilirubin**

Any participant with a graded elevation in total bilirubin will undergo a diagnostic work up that includes right upper quadrant ultrasound, testing for gamma glutamyl transferase (GGT) HAV (IgM and IgG), HBV (hepatitis B surface antigen and IgM anti-hepatitis B core antigen), HCV (anti-hepatitis C antibody and HCV PCR), EBV (IgM and IgG VCA and EBNA antibodies), CMV (IgM and IgG), VZV (IgM and IgG) and HSV (IgM and IgG), and any other relevant laboratory tests as determined by the investigators. Participants will be referred for evaluation by a hepatologist in the event of ALT or AST increase equal to or greater than 3x the upper limit of normal with concurrent increase in total bilirubin equal to or greater than 2x the upper limit of normal, and if otherwise clinically indicated.

These evaluations will be of no cost to the participant.

### **6.2.12 Antiretroviral and Immunogenicity Assessments**

HIV-1 levels will be assessed by (Appendix A):

1. Standard HIV-1 viral load assay (Cobas Taqman) (CLEP-certified) will be performed at a contracted laboratory, LabCorp (RUH site) and at the AUH and CUH clinical virology labs. The detection range of the assay is 20-10x10^6 copies/ml. HIV-1 viral load will be determined at multiple time points before and after 3BNC117 administration.
2. Transcription mediated amplification is a qualitative method to detect plasma HIV-1 RNA (Procleix Ultrio Plus, Genprobe). It has 50% sensitivity at 3.8 copies/mL and 95% sensitivity at 12 copies/mL. TMA results are considered binary and defined as positive or negative according to assay outcomes.
3. Single copy assay has a detection limit of 1-2 copies HIV-1 RNA/mL of plasma. This assay will be performed in the Laboratory of Molecular Immunology. This

assay will be performed on samples collected at baseline (week -2 and day 0), and 1 day after the second romidepsin infusion in each treatment cycle.

4. HIV-1 cell-associated unspliced HIV-1 RNA dd PCR assay. This assay provides an accurate quantification of HIV-1 transcriptional activity and will be performed at the AUH site. This assay has a limit of detection of 1 HIV-RNA copy per 1 million CD4+ T cells.
5. HIV-1 cell associated DNA levels in CD4+ T cells will be measured at the AUH site, before and after administration of 3BNC117. This assay has a limit of detection of 10 DNA copies per 10^6 CD4+ T cells. This assay will be performed at the AUH site.
6. The size of the functional HIV-1 reservoir will be determined by the number of infectious unit per 10^6 resting memory CD4+ T cells (IUPM) using a viral outgrowth assay before (week -2) and after therapy, just before ATI (week 22).

Given the large number of cells required for this assay, viral outgrowth assays will not be performed at a later time point. The size of the reservoir in participants who remain virologically suppressed during ATI or are re-suppressed following ART resumption will be evaluated by levels of cell-associated HIV-1 DNA, performed at week 48.

In addition, the effects of 3BNC117 on host immune responses and on circulating HIV-1 strains will be evaluated by the following assays (Appendix A):

7. TZM-bl neutralization assay will be performed in the laboratory of [name] of the Beth Israel Deaconess Hospital in Boston (a Core Laboratory sponsored by the Collaboration for AIDS Vaccine Discovery, CAVD). *In vitro* neutralization assays will be performed with serum from study subjects before and after administration of 3BNC117.
8. Phenotypic characteristics for T and NK cells using standard cell marker panels by flow cytometry (e.g. CD3, CD4, CD8, CD45RA, CCR7 for T cells and CD16/CD56 for NK cells) will be determined before and after each treatment cycle. These assays will be performed at the RUH and/or AUH sites.
9. Functional properties of cytotoxic T cells and NK cells before and after each treatment cycle will be investigated by analyzing cytokine secretion properties (e.g. IL-2, IFN- $\gamma$ , TNF- $\alpha$ ) and surface expression of CD107a/b as a surrogate marker of cytotoxic activities. CD69, CD161, NKp46, NKG2, and CD85J expression will be analysed on NK cells. In addition, change from baseline in the capacity of NK and CD8+ T cells to mediate inhibition of viral replication *ex vivo* will be analyzed. These assays will be performed at the RUH site and the laboratory of [name] at the Vaccine Research Center (VRC) at NIH, a core lab of the Collaboration for AIDS Vaccine Development (CAVD).

10. Levels of inflammation markers, such as C-reactive protein, D-dimers, IL-6, and soluble CD14 will be performed in plasma or serum samples, prior to and after 3BNC117 infusions. These will be performed at the Laboratory of Molecular Immunology, or by clinical assays at LabCorp.
11. Sequencing – If latently infected virus can be isolated/cultured ex-vivo, sequencing and phylogenetic analysis of HIV-1 env will be performed in samples collected before and after the first and second treatment cycles and at the time of virologic rebound. These analyses will use similar approach to the reported in Caskey et al (2015) and Schoofs et al (2016). This will allow us to compare viruses grown from PBMCs collected from subjects while on ART to rebound viruses collected after treatment interruption and analyze the induction of escape mutations. This will be performed at the RUH and/or the UCH site.
12. Genotypic analysis of antiretroviral resistance in rebounding viral strains (with HIV-1 RNA levels > 400 copies/ml) will be performed by clinical assays at all sites.
13. Evaluation of HIV-1 integration sites by deep sequencing will be performed at the RUH site, before and after the first and second treatment cycles.

Pharmacokinetics and immunogenicity assays (Appendix A):

14. Measurement of 3BNC117 levels by validated sandwich ELISA using a murine anti-idiotypic antibody to 3BNC117 and will be performed at Celldex Therapeutics. 3BNC117 levels will be measured in serum or plasma.
15. Anti-drug (3BNC117) antibody responses in serum or plasma. Validated Assays will be performed at Celldex Therapeutics Inc.
16. Measurement of romidepsin levels by validated sandwich ELISA will be performed on samples collected before, at the end of the infusion, and 1 day after each romidepsin infusion during treatment cycle 1.

Research samples collected at all clinical sites will be processed and stored locally, until samples are transferred to a pre-determined site for specific assays, as outlined above. Optimal sample collection, processing, cryopreservation, archiving and storage will be maintained. Additional studies will be performed as warranted at the discretion of the investigators.

### **6.2.13 Pharmacokinetic evaluations**

Pharmacokinetic parameters will be calculated using standard non-compartmental analysis methods. Descriptive results will be presented for the pharmacokinetic parameters.

3BNC117 PK assessments will be performed on plasma or serum samples in Group A before the first 3BNC117 and at multiple time points as outlined in the Time of Events Schedule (Appendix A). Romidepsin PK assessments will be performed on plasma or serum samples. These measurements will be performed during the first treatment cycle at baseline, end of infusion, and 1 day after each romidepsin infusion.

## **7 Investigational Products**

- 3BNC117 is manufactured by Celldex Therapeutics, Inc. 3BNC117 is a recombinant, fully human monoclonal antibody (mAb) of the IgG1 $\kappa$  isotype that specifically binds HIV envgp120. 3BNC117 is being investigated under USFDA IND 118,225.

- Romidepsin (Istodax®) is manufactured by Celgene Corporation. This histone deacetylase (HDAC) inhibitor is a bicyclic depsipeptide.

### **7.1 Regimen**

- 3BNC117 will be administered intravenously at 30 mg/kg dose level on day 0 and day 56 (Group A only).

- Romidepsin will be administered intravenously at 5 mg/m^2 dose level on days 2, 9, 16, 58, 65, and 72 for Group A and days 0, 7, 14, 56, 63, and 70 for Group B.

### **7.2 Storage and Shipment of the Investigational Products**

- 3BNC117 will be shipped from Celldex Therapeutics and will be stored in the site research pharmacy at 2- 8°C. 3BNC117 is a clear liquid, provided in single-use vials containing 5 ml of product at 20 mg/ml concentration. For further information refer to the 3BNC117 IB.

- Romidepsin will be provided by Celgene Corporation and will be stored in the site research pharmacy. At room temperature, romidepsin is a white powder. For further information refer to the romidepsin IB.

### **7.3 Dispensing and Handling of the Investigational Products**

- 3BNC117 will be dispensed by the site research pharmacy. Trial personnel will ensure that the study ID number on the piggy-back matches the study ID assigned to the volunteer prior to administration.

3BNC117 will be provided in single-use vials containing 5 ml of 3BNC117 at a 20 mg/ml concentration. The appropriate dose will be calculated by the site research pharmacist according to subject's weight. 3BNC117 will be dispensed in a piggy-back, and diluted in normal saline (NaCl 0.9%), to a volume of 250 ml. It will be dispensed ready for administration by the study investigators and be good for infusion for 3 hours.

- Romidepsin will be dispensed by the site research pharmacy. Trial personnel will ensure that the study ID number on the piggy-back matches the study ID assigned to the volunteer prior to administration.

#### **7.4 Accountability and Disposal of Used and Unused Investigational Product**

The date, allocation number and location of storage of the vials will be recorded in a log at each study site. During the trial, the product accountability form, and the dispensing log will be monitored. At the end of the trial, unused 3BNC117 vials will be returned to Celldex Therapeutics or destroyed; unused romidepsin vials will be returned to Celgene Corporation or destroyed.

#### **7.5 Concomitant and Prohibited Medications**

- As per the manufacturer of romidepsin, the prophylactic use of antiemetics such as ondansetron is strongly encouraged.

- Any medications listed in Appendix E, which may cause QTc prolongation or induce torsades de pointes should not be used.

- Concomitant use of CYP3A4 or Pgp inhibitors with romidepsin should be avoided (excluding granisetron and ondansetron) to prevent potential increase in romidepsin exposure during concomitant treatment with these drugs. Should a patient already enrolled on this study require treatment with these drugs (as listed in Appendix F) romidepsin must be interrupted prior to starting these drugs and should not resume until a washout period of at least 5 half-lives has elapsed. All participants taking protease inhibitors, which are strong inhibitors of P450 3A4, will be switched to an integrase inhibitor prior to enrollment. In addition, participants on regimens that contain cobicistat (a CYP3A4 and Pgp inhibitor) will be switched to an integrase inhibitor-based regimen that does not include cobicistat.

- Any medications that have the potential to alter serum electrolytes (e.g., diuretics) should be monitored very closely for electrolyte abnormalities as these can contribute to the risk of QT prolongation and ventricular arrhythmias.

- Romidepsin can prolong PT and elevate INR in patients receiving warfarin. Patients on warfarin will be excluded from the study.

### **8 Data Analysis**

#### **8.1 Analysis of Antiretroviral effects, Safety and Pharmacokinetics**

##### **Primary Endpoint:**

1. Days to viral rebound during ATI or days to reinitiation of ART in participants who restart ART before viral rebound. Viral rebound is defined as HIV-1 RNA  $\geq$  200 copies/ml on 2 consecutive measurements during ATI. If viral rebound occurs, the

date of the first measurement of HIV-1 RNA  $\geq 200$  copies/mL will be defined as “date of viral rebound.” As primary analysis, we will use the Wilcoxon-Mann-Whitney test to compare the median time to viral rebound between the two study groups. As secondary analysis, we will use the Kaplan-Meier estimator and log-rank test to assess the significance of the difference between the survival curves in the two study arms.

## **Secondary and Exploratory Endpoints:**

### 1. Safety evaluation:

The number and percentage of subjects experiencing one or more AEs will be summarized by relationship to study drug, and severity. AEs will also be summarized by severity grade and by relationship to study drug according to the CTCAE v4.03 and DAIDS v2.0 grading scale. Changes will be calculated relative to the values collected at baseline.

### 2. Size of the functional HIV-1 reservoir:

The size of the functional HIV-1 reservoir will be determined by the number of infectious unit per  $10^6$  resting memory CD4+ T cells (IUPM) using a viral outgrowth assay before (week -2) and after therapy, just before ATI (week 22). Paired student t-test or paired Wilcoxon test will be used to determine changes in reservoir size from baseline to the pre-ATI time-point for each group.

Total HIV-1 DNA, episomal HIV-1 DNA (2-LTR), and unspliced HIV-1 RNA in circulating total CD4+ T cells will also be determined at baseline (week -2, week 0), before and after each treatment cycle, at the pre-ATI time point (week 24), and at the end of the study (week 48). A 95% repeated measures ANOVA F-test will be used to compare changes in these variables during the study.

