Study Duration	50 weeks per participant; total planned study duration 24 months
Objectives	
Primary Objective:
 
 
- Evaluate the effects of romidepsin plus 3BNC117 or romidepsin alone on delaying or preventing viral rebound in HIV-1-infected individuals during an analytical interruption of ART.
 
 
Secondary Objectives:
 
 
- Evaluate the safety of romidepsin plus 3BNC117 or romidepsin alone in ART-treated HIV-1 infected individuals;
 
- Evaluate the effects of romidepsin plus 3BNC117 or romidepsin alone on the size of the replication competent HIV-1 reservoir in ART-treated HIV-1-infected individuals;
 
- Evaluate the immunomodulatory effects of romidepsin plus 3BNC117 or romidepsin alone in ART-treated HIV-1-infected individuals.
 

Number of Subjects	30 (15:15)

Study Population	HIV-infected males and females, between the ages of 18-65, on ART for at least 24 months, with HIV-1 RNA plasma level of < 50 copies/ml by standard assays for at least 18 months, and with current CD4+ T cell counts > 500 cells/ $\mu$ l.

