
Statistical Methodology
	
The Wilcoxon-Mann-Whitney will be used to determine changes from baseline to the pre-ATI time-point in reservoir size for each group. Fishers exact or chi-square test will be used to compare the proportion of subjects in both groups with detectable viremia during each romidepsin treatment. Functional properties of cytotoxic T cells and NK cells will be correlated to changes in total HIV-1 DNA and IUPM. Flow cytometry data will be evaluated by Boolean partitioning of NK and T cell responses into distinct responding populations (Lamoreaux et al., 2006).
 
Finally, correlation analysis will be performed to identify the markers most likely associated with time to viral rebound. As exploratory analysis, a linear regression model will be used to determine predictors of log-transformed time to viral rebound in both arms. P values <math><0.05</math> will be considered statistically significant.

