This study will address several gaps in current knowledge: 1) The effect of combining ART+LRA+bNAb vs. ART+LRA alone on the size of the HIV-1 reservoir and time to viral rebound following ART interruption; 2) The impact of repeated exposure to a potent LRA with an interval of 2 months; 3) Correlates for time to viral rebound in patients receiving LRAs and combined LRA+bNAb; 4) The immunomodulatory effects of LRA and bNAb treatment by characterizing phenotypic as well as functional changes in antigen-presenting (DCs, macrophages/monocytes) and effector cells (NK, NKT, CD8+ cells).

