#### Secondary Objectives:

- Evaluate the safety of romidepsin plus 3BNC117 or romidepsin alone in ART-treated HIV-1 infected individuals;
- Evaluate the effects of romidepsin plus 3BNC117 or romidepsin alone on the size of the HIV-1 reservoir in ART-treated HIV-1-infected individuals;

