### 3. Plasma HIV-1 RNA:

Plasma HIV-1 RNA levels will be measured by a routine clinical assay (Cobas Taqman; detection limit 20 copies/mL), a transcription mediated amplification (TMA)-based assay (detection limit 12 copies/mL) and/or a single copy assay (detection limit 1-2 copies/mL). Fishers exact or chi-square test will be used to compare the proportion of subjects in both groups with detectable viremia during each romidepsin treatment.

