### 4. Host immune responses:

Functional properties of cytotoxic T cells and NK cells will be correlated to changes in total HIV-1 DNA and IUPM. Flow cytometry data will be evaluated by Boolean partitioning of NK and T cell responses into distinct responding populations (Lamoreaux et al., 2006).

Finally, linear regression will be used to identify predictors of log-transformed time to viral rebound in both arms. P values  $<0.05$  will be considered statistically significant.

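### No between-arm comparison of the change in IUPM is specified, and the synopsis and section 8.1 name different tests for the within-group change

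*Combined protocol and SAP*

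**What the plan says.** **Question.** Section 3.1.1 lists among the gaps to be addressed "The effect of combining ART+LRA+bNAb vs. ART+LRA alone on the size of the HIV-1 reservoir". The formal objectives are looser. Section 3.3 has "Evaluate the effects of romidepsin plus 3BNC117 or romidepsin alone on the size of the HIV-1 reservoir", and the synopsis version refers to effects "on the size of the replication competent HIV-1 reservoir in ART-treated HIV-1-infected individuals". Section 3.5 makes IUPM before and after therapy a secondary endpoint.

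**IUPM analysis.** Under item 2 of the secondary endpoints in section 8.1, IUPM is measured at week -2 and week 22. A paired t-test or a paired Wilcoxon test "will be used to determine changes in reservoir size from baseline to the pre-ATI time-point for each group". No rule is given for choosing between the two. The synopsis says: "The Wilcoxon-Mann-Whitney will be used to determine changes from baseline to the pre-ATI time-point in reservoir size for each group". The only other analysis that uses IUPM is a correlation: "Functional properties of cytotoxic T cells and NK cells will be correlated to changes in total HIV-1 DNA and IUPM".

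**Other markers.** For total HIV-1 DNA, 2-LTR circles and unspliced RNA, section 8.1 says: "A 95% repeated measures ANOVA F-test will be used to compare changes in these variables during the study". It names no arm or arm-by-time term, and the listed time points include week 48. For plasma RNA the plan does compare arms: it will "compare the proportion of subjects in both groups with detectable viremia" by Fisher's exact or chi-square test.

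**The concern.** The trial is randomised 1:1 and the romidepsin-only arm exists to isolate the contribution of 3BNC117. For IUPM, though, the specified output is two separate tests of change, one per arm. A significant result in one arm and not in the other is not evidence of a difference, and the same verdict in both is not evidence of similarity. In an open-label study, a contrast left unspecified can be chosen after the data are seen, together with the choice of paired test and the handling of negative cultures.

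The test named in the synopsis adds a conflict. If it is applied literally to pre and post values from the same people, it ignores the pairing and loses power. If it was meant as a between-arm test of change, it contradicts section 8.1 and its own reference to each group. It may be only a naming slip, but the two texts cannot both be followed.

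**Working it through.** **Inputs from the plan.** Section 8.2 gives 12 per arm for analysis and 15 per arm enrolled. Its own power figure reproduces: effective n = 12 × 0.864 = 10.4 per arm, d = 13/10 = 1.3, two-sided 5%, noncentral t, power 80.1% against the stated 80%. That figure concerns time to rebound. No SD, correlation or power is given for IUPM.

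**Assumed inputs.** log10 IUPM is normal with SD 0.5 at both visits, pre/post correlation r is 0.5, 0.7 or 0.85, and the test is an exact signed-rank at two-sided 5% (40,000 simulated trials). Without censoring, the verdicts depend only on the ratio of the drop to the SD, so a different SD rescales the drops below.

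**1. Same true drop in both arms.** If each within-arm test has power p, exactly one arm is significant with probability 2p(1−p), which peaks at 0.5 when p = 0.5. For a drop of 0.3 at n = 12, p = 0.432, 0.637 and 0.907 for the three correlations:

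- 2 × 0.432 × 0.568 = 0.491
- 2 × 0.637 × 0.363 = 0.462
- 2 × 0.907 × 0.093 = 0.169

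The simulated values are 0.490, 0.465 and 0.168. Probability that exactly one arm is significant, for r = 0.5 / 0.7 / 0.85:

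| True drop, log10 | 12 per arm | 15 per arm |
|---|---|---|
| 0 | 0.080 / 0.083 / 0.083 | 0.094 / 0.090 / 0.090 |
| 0.1 | 0.154 / 0.198 / 0.300 | 0.187 / 0.248 / 0.372 |
| 0.2 | 0.342 / 0.444 / 0.484 | 0.409 / 0.491 / 0.400 |
| 0.3 | 0.490 / 0.465 / 0.168 | 0.491 / 0.352 / 0.060 |
| 0.5 | 0.255 / 0.054 / 0.001 | 0.113 / 0.011 / 0.000 |

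A Wilcoxon-Mann-Whitney test on the individual changes rejects in 4-5% when the arms are identical. Setting 20% of baseline values to the detection limit gives a similar picture at 12 per arm: 9%, 16-28%, 32-50%, 31-50% and 2-37% for the five rows.

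**2. Arms truly different.** For drops of 0.6 and 0.3, both arms give the same verdict in 44-91% of trials (n = 12) or 55-97% (n = 15). For 0.3 against 0 the figures are 13-56% and 8-45%.

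**3. Synopsis followed literally.** For a drop of 0.3, an unpaired test of pre against post values has power 0.208 / 0.175 / 0.151 at n = 12, against 0.432 / 0.637 / 0.907 for the signed-rank test. At n = 15 it has 0.279 / 0.253 / 0.235 against 0.556 / 0.774 / 0.969.

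**4. What a between-arm analysis can deliver.** By the minimum-ARE method of section 8.2, 80% power needs a difference of 1.30 SD of the change at n = 12 and 1.15 SD at n = 15. The SD of the change is 0.5 × √(2(1−r)) = 0.500, 0.387 or 0.274 log10. At n = 12, 1.30 SD is therefore 0.65, 0.50 or 0.36 log10.

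For ANCOVA, the 95% CI factor on the A/B ratio is 10^(t × 0.5 × √(1−r²) × √(2/n)) with 2n−3 degrees of freedom. At n = 12 and r = 0.5, the exponent is 2.08 × 0.433 × 0.408 = 0.367, a factor of 2.33. All three correlations give 2.33 / 2.01 / 1.67 at n = 12 and 2.11 / 1.85 / 1.58 at n = 15. Adding two degrees of freedom for site changes these by 0.01 at most.

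**5. Week 48.** Sections 3.5 and 8.1 schedule HIV-1 DNA at week 48 without restriction, and section 6.1.7 keeps participants who rebound in follow-up to that week. Section 6.2.12 describes the week-48 evaluation for people who stayed suppressed or were re-suppressed, without saying that others are left out. One ANOVA through week 48 also mixes pre-interruption values with values taken after the interruption and after differing times back on ART.

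**The case against.** The formal objectives can be read as asking about each regimen separately, and a per-group paired test answers that reading. The explicit contrast on the reservoir stands only in a background list; the hypothesis in section 3.2 is comparative for viremia during the interruption, which has its own test. The plan nowhere says that an arm difference will be inferred from two p-values, so the discordance figures describe a likely misreading and are not an error rate of a specified test. They also rest wholly on assumed inputs.

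The proposed test is weak too. For a true difference of 0.3 log10, a between-arm Wilcoxon-Mann-Whitney test has power of about 0.26 / 0.40 / 0.69 at 12 per arm, so it misses that difference in 74% / 60% / 31% of trials. The synopsis wording may be a slip, the ANOVA does not exclude an arm term, and the schedule appendices, which were not in the text reviewed, may settle who is sampled at week 48.

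Most of this stands, and it sets the weight of the point. It confines the matter to secondary endpoints, makes estimation rather than testing the reason for the change, and reduces the week-48 part to a request for clarification. It does not supply the missing contrast or reconcile the two test names.

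**Conclusion.** The concern holds. As written, the plan provides no estimate of the randomised difference in IUPM change, and the synopsis and section 8.1 assign different tests to the same within-group change. Both follow from the text and need no numerical assumption.

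The size of the interpretive risk does depend on assumptions. Under those used here, two arms with the same true change would disagree in significance in anything from almost none to about half of trials; half is the ceiling, not the typical value. For HIV-1 DNA, 2-LTR and unspliced RNA the gap is smaller, because the ANOVA could carry an arm term but does not name one. This should be fixed. The primary and safety analyses are not affected.

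**What to change.** - Prespecify one between-arm IUPM estimate with a 95% CI and present it as estimation. Choose either ANCOVA of week-22 log10 IUPM on arm and week -2 log10 IUPM (site, the stratification factor, may be added), or a Wilcoxon-Mann-Whitney test on individual changes with a Hodges-Lehmann estimate.
- State how zero or below-detection outgrowth is handled.
- Keep the within-arm paired test as descriptive, say which paired test it is, and use the same wording in the synopsis and section 8.1.
- For HIV-1 DNA, 2-LTR and unspliced RNA, name the arm contrast at week 24. Report week 48 separately, stating who is included and the number contributing per arm.

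The cost is wording in the synopsis and section 8.1 plus minor analysis work, with no new samples or visits. The price is a visibly wide confidence interval.

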## **3 Objectives and Rationale**

### **3.1 Introduction**

#### **3.1.1 Background**

Despite the major success of combination antiretroviral therapy (ART) in suppressing viral replication and preventing disease progression, HIV-1 infection persists and is not eliminated by available antiretroviral drugs. When ART is discontinued, viral rebound occurs within 2-3 weeks in most subjects (Davey et al., 1999) (Strategies for Management of Antiretroviral Therapy Study et al., 2006). Even in the context of suppressive ART, HIV infection is characterized by persistent low level HIV-1 viremia and immune activation and cell-associated HIV-1 remain relatively stable (Deeks et al., 2013). Studies have shown that intensified antiretroviral regimens do not affect low level viremia and do not result in lower levels of HIV-1 persistence (Markowitz et al., 2014; McMahon et al., 2010).

The primary barrier preventing HIV-1 eradication by ART is a pool of long-lived latently infected memory CD4+ T-cells (Chomont et al., 2009; Finzi et al., 1997). These cells harbor silent integrated proviral DNA capable of resuming HIV-1 expression upon activation (Archin et al., 2009; Bosque and Planelles, 2009; Finzi et al., 1999). In the inactive, resting state these cells cannot be recognized or eliminated by the immune system or antiretroviral drugs. Importantly, latently HIV-1 infected cells can be induced

to resume HIV-1 expression by latency reversing agents (LRAs) (Ylisastigui et al., 2004). This in turn could expose infected cells to immune-mediated recognition and killing.

Recent clinical trials have demonstrated proof-of-concept that the state of HIV-1 latency can be disrupted safely in patients on ART by a group of LRAs called histone deacetylase inhibitors (HDACi) (Archin et al., 2012; Elliott et al., 2014). However, the outcome of these trials plus an accumulating body of ex vivo research also suggest that, in the majority of patients, reactivation alone does not reduce the HIV-1 reservoir - possibly because of insufficient immune mediated killing of reactivated cells (Ho et al., 2013; Shan et al., 2012). This calls for combining LRAs with immune targeted interventions such as HIV-1-specific monoclonal antibodies.

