### 3.5 Secondary Endpoints

- Safety evaluation, as measured by rate and severity of adverse events (AE), serious adverse events (SAE), and serious unexpected serious adverse reactions (SUSAR).
- Size of the functional, latent HIV-1 reservoir as determined by the number of infectious units per  $10^6$  resting memory CD4+ T cells (IUPM) using a viral outgrowth assay before and after therapy. Post therapy measurements will occur after the second cycle, just before ATI. These measurements will be performed in [name] laboratory.
- Size of the proviral HIV-1 reservoir as determined by total HIV-1 DNA and episomal HIV-1 DNA (2-LTR) in circulating total CD4+ T cells at baseline, after each romidepsin cycle, prior to the ATI period (week 24), and at the end of the study (week 48).
- Plasma HIV-1 RNA, as measured by a routine clinical assay (Cobas Taqman; detection limit 20 copies/mL), a transcription mediated amplification (TMA)-based assay (detection limit 12 copies/ml) and/or a single copy assay (detection limit 1-2 copies/mL).

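### The F-test for HIV-1 DNA, 2-LTR DNA and unspliced RNA includes week 48, so a change over time cannot be separated from the effect of the treatment interruption

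*Combined protocol and SAP*

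**What the plan says.** Section 8.1, under the functional reservoir endpoint, contains two analyses.

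- **IUPM by viral outgrowth.** It is measured at weeks -2 and 22. For the paired comparison, by t-test or Wilcoxon, the plan says that it "will be used to determine changes in reservoir size from baseline to the pre-ATI time-point for each group".
- **The other three markers (total HIV-1 DNA, 2-LTR DNA and unspliced RNA).** These are measured at weeks -2 and 0, before and after each cycle, "at the pre-ATI time point (week 24), and at the end of the study (week 48". The only analysis stated is: "A 95% repeated measures ANOVA F-test will be used to compare changes in these variables during the study". No contrast, arm term, pre-ATI limit or handling of rebound is given.

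Section 3.5 makes total and 2-LTR DNA, week 48 included, a secondary endpoint. Unspliced RNA is exploratory (section 3.6). The objective they serve (section 3.3) is: "Evaluate the effects of romidepsin plus 3BNC117 or romidepsin alone on the size of the HIV-1 reservoir in ART-treated HIV-1-infected individuals". The synopsis defines reservoir-size change in each group as baseline to the pre-ATI time point.

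Section 6.1.7 stops ART at week 24 and resumes it after two consecutive values of at least 200 copies/ml. Section 3.1.1 says: "When ART is discontinued, viral rebound occurs within 2-3 weeks in most subjects". Section 6.2.12 describes the week 48 DNA measure as reflecting "The size of the reservoir in participants who remain virologically suppressed during ATI or are re-suppressed following ART resumption". The F-test sentence carries no such condition.

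**The concern.** The objective concerns the reservoir in people on ART who have received the study drugs. Every time point through week 24 fits that description. Week 48 does not: in between, ART is stopped, virus is expected to return, and ART is restarted. One omnibus test over all the time points asks only whether the marker was constant. A rejection does not show whether the change came with the treatment cycles or after the interruption. Nor does the test give direction, so a rise at week 48 that offsets an earlier fall could hide that fall from anyone reading the change across the whole study. At stake is the interpretation of a secondary endpoint and one exploratory endpoint. The primary endpoint is untouched.

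**Working it through.** **1. The plan's own figure.** The documents give no figure for this F-test. Section 8.2 does supply the SD and target effect used in step 2, so its calculation is checked first.

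- Inputs: 12 per arm, 13 days, SD 10, 5% (taken as two-sided), minimum asymptotic relative efficiency 0.864.
- Effective total: 2 × 12 × 0.864 = 20.74, so df = 18.74.
- Noncentrality: 1.3 × √(20.74/4) = 2.96.
- Power: 80.1%, as stated. Allowing for 20% dropout, 12/(1 − 0.20) = 15 per arm, also as stated.

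**2. What precedes the week 48 sample.** Inputs: ART stops at week 24; rebound at 14-21 days (section 3.1.1); weekly viral load; confirmation assumed one week later, with prompt restart.

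| Mean time to rebound | Rebound (week) | Confirmed (week) | Weeks back on ART at week 48 |
|---|---|---|---|
| 14-21 days | 26-27 | 27-28 | 20-21 |
| 27-34 days (13-day effect added) | 27.9-28.9 | 28.9-29.9 | 18-19 |

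With SD 10 and a normal distribution (assumed), the proportion rebounding by week 36 (day 84) in the slowest case is Φ((84 − 34)/10) = Φ(5), over 99.9%. On these inputs, week 48 follows rebound and restart for nearly everyone.

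**3. The within-group time test when only week 48 moves.** Assumptions: 7 time points (weeks -2 and 0, after cycle 1, before and after cycle 2, weeks 24 and 48), independent errors, no change through week 24, and a week 48 shift of δ within-person SDs in everyone. The noncentrality is λ = n δ² (k − 1)/k, with k − 1 = 6 and 6(n − 1) degrees of freedom. For n = 15 and δ = 1, λ = 15 × 6/7 = 12.86 on 6 and 84 df, giving 74%.

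| δ | n = 15 | n = 12 |
|---|---|---|
| 0 | 5% | 5% |
| 0.5 | 20% | 17% |
| 1 | 74% | 61% |
| 1.5 | 99% | 95% |

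Simulation gives the same rates to within about 1 percentage point.

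**4. Two arms.** Simulation of 3,000 trials per setting, with 12 per arm, within-person SD 0.15-0.25 log10, no drug effect, and a week 48 shift in rebounders only. SDs and shifts are assumed.

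| Assumed shift (log10) | Time test, week 48 included, all rebound | Time test ending at week 24 |
|---|---|---|
| 0.1 | 21-57% | about 5% |
| 0.2 | 76-100% | about 5% |
| 0.3 | 99-100% | about 5% |

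With week 48 included, the arm-by-time test stays at about 5% when all participants in both arms rebound. It is about 6-11% when 75% rebound in one arm and 100% in the other.

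**The case against.** The strongest reply is that the plan already has the right window where it matters most. The functional reservoir measure stops at week 22, and the synopsis defines reservoir-size change as baseline to pre-ATI. This stands for IUPM, and it limits the point to the three markers under the F-test. It does not rescue the F-test, because section 8.1 applies that test across the study without such a limit.

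A second reply is that section 6.2.12 directs the week 48 DNA reading to participants who are suppressed or re-suppressed, and typical rebounders would have about 18-21 weeks back on ART. That reduces the chance of active viremia at the reading. It does not make the reading comparable with week 24, because an interruption still lies between the two.

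A third is that both arms stop ART, so the randomized comparison is largely protected. This also stands. The arm comparison is affected only if the arms differ in rebound or time off ART. The hypothesis predicts such a difference, but the illustrated effect is small.

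Some stronger readings are tempting but unsupported:

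- A reader might infer that the plan counts interruption viremia as a drug effect. It names no contrast and makes no such attribution.
- A reader might infer that people who rebound in the optional week 36-48 extension cannot be re-suppressed by week 48. The documents give no re-suppression time, and rebound at week 37 confirmed at week 38 would leave about 10 weeks on ART.
- A reader might infer that such people would be lost from the whole analysis as incomplete cases. No missing-data rule is stated.

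**Conclusion.** The concern holds for total HIV-1 DNA, 2-LTR DNA and unspliced RNA, mainly for the within-group time effect. Followed as written, the test cannot distinguish change during the treatment cycles from change after ART was stopped. The timing conclusion rests on the plan's 2-3 weeks to rebound, its SD of 10 days and its 13-day target, with normality and prompt restart assumed. The 2-3 weeks comes from background literature on interruption in general, but adding the 13-day target for the combination arm does not change the conclusion. The rejection rates are illustrative: they assume a shift the documents do not give, and they show how readily the test responds to week 48, not how often a false result would occur in this trial. The masking of a pre-ATI decline is a possibility and is not quantified here. The figures do not support a claim that the arm comparison is seriously biased, or that the reservoir analysis as a whole is compromised. The change is worth making before analysis.

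**What to change.** In section 8.1:

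- Restrict the repeated measures F-test for these markers to the on-ART period, week -2 to week 24, and include an arm-by-time term.
- Name baseline to week 24 as the contrast answering the reservoir objective for total HIV-1 DNA and 2-LTR DNA.
- Analyse unspliced RNA over the same window as the exploratory transcription endpoint, not as a reservoir measure.
- Report week 48 separately and descriptively as change from week 24, by rebound status and time since ART restart.

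This brings the DNA analyses into line with the window used for IUPM and in the synopsis. It costs only wording, since all samples are already planned. The downside is that week 48 no longer contributes to the formal test.
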